9 STATISTICAL CONSIDERATIONS

9.1 STATISTICAL HYPOTHESES

We have two primary hypotheses (H1 and H2):

H1: Combination treatment with and without health care professional support is more effective than duloxetine monotherapy in improving BPI GPS.

The primary comparison will be the combination treated groups (with and without health care professional support) vs. duloxetine group.

H2: Combination treatment with health care professional support is more effective than combination treatment without health care professional support in improving BPI GPS.

The primary comparison will be combination group with health care professional support vs. without health care professional group.

Exploratory hypothesis: Compared to those without comorbid psychological distress, participants with comorbid psychological distress are more likely to respond to combination therapy (with and without health care professional support) than to duloxetine monotherapy.

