9.2 SAMPLE SIZE DETERMINATION

With 280 participants and 20% loss to follow-up, we will have 75 evaluable participants in each treatment group. Based on published literature (*Kroenke K et. al JAMA July 2014*), the estimated standard deviation (SD) for BPI GPS score is 2.2. Assuming a moderate correlation of 0.5 between baseline and follow-up measures, we estimate that the SD in an analysis of covariance (ANCOVA) will be approximately 1.9. Therefore, we will have 90% power to detect a difference of -1 in BPI GPS score between combination groups (n= 150) and drug only group (n=75) for Aim 1. The power will be 83% power for comparison between combination with health care professional (n=75) and combination without health care professional (n=75) for Aim 2. All power calculations are based on two-sided t tests with alpha level of 0.025 to adjust for Bonferroni correction of testing two main hypotheses.

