9.4.2 ANALYSIS OF THE PRIMARY ENDPOINT(S)

Primary Outcome

The primary outcome of the study is BPI GPS score collected at Weeks 13 and 25. BPI GPS is a self-report measure of pain severity and interference with proven reliability and validity across different pain conditions. The overall score is defined as the average of 11 items. Two subscales are also defined: BPI pain severity and BPI pain interference. BPI pain severity is the average of 4 items asking about current pain and worse, least, and average pain in the past week. BPI pain interference is the average of 7 items that rate how pain interferes with various activities (higher score indicate greater pain interference). All study participants will be analyzed according to randomized treatment assignment regardless of adherence to the treatment protocols. We have two primary hypotheses (H1 and H2):

H1: Combination treatment with and without health care professional support is more effective than duloxetine monotherapy in improving BPI GPS.

H2: Combination treatment with health care professional support is more effective than combination treatment without health care professional support in improving BPI GPS.

Research has shown that the use of ANCOVA with baseline measure as a covariate is an optimal method in both design and analysis of trials with a continuous primary outcome. Compared to the use of change score as the primary outcome, ANCOVA is generally superior in terms of efficiency, precision, and power. Therefore, the primary analysis will be Week 13 and 25 BPI scores as a primary outcome while adjusting for baseline measurement.

In primary analysis, we will fit a LMM to account for the correlation among the repeated measures. The model will include indicator variables for intervention arms, visit, and the interaction term. Covariates will include the pre-randomized measure of BPI global score, the stratification factor opioid use, and the number of pain sites. Average follow-up BPI global pain scores for the 3 intervention groups will be estimated using least square means. Two different contrasts will be constructed to test H1 and H2 separately, each at the significance level of 0.025.

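### Testing H1 and H2 each at a fixed 0.025 is valid, but Holm's step-down has more power at the same 5% family-wise bound

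*Combined protocol and SAP*

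**What the plan says.** Section 9.1 names two primary hypotheses with one comparison each. For H1, "The primary comparison will be the combination treated groups (with and without health care professional support) vs. duloxetine group". For H2 it is combination treatment with support against combination treatment without it.

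Section 9.4.2 fits one linear mixed model to the week 13 and week 25 scores, adjusted for baseline. It states that "Average follow-up BPI global pain scores for the 3 intervention groups will be estimated using least square means", and then that "Two different contrasts will be constructed to test H1 and H2 separately, each at the significance level of 0.025".

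Section 9.2 gives the reason for 0.025: "All power calculations are based on two-sided t tests with alpha level of 0.025 to adjust for Bonferroni correction of testing two main hypotheses". It also states that "we will have 90% power to detect a difference of -1 in BPI GPS score between combination groups" (150) and the drug-only group (75), and gives 83% for Aim 2 (75 against 75). No step-down, gatekeeping or other rule that passes on unused alpha appears anywhere.

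**The concern.** A fixed split leaves error unspent. Once one hypothesis has been rejected at 0.025, the other can be tested at 0.05 without breaking the 5% family-wise bound, and the plan does not use this. Aims 1 and 2 ask separate questions, and the trial wants an answer to both. A result with one p-value below 0.025 and the other between 0.025 and 0.05 would count as a single success under the current rule and as two under Holm. The larger gain falls on H2, the hypothesis with the lower power. Section 9.4.2 justifies ANCOVA on grounds of efficiency and power, and the same reasoning applies here.

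**Working it through.** **Inputs from Section 9.2.** SD 2.2; baseline to follow-up correlation 0.5; ANCOVA SD 2.2 × √(1 − 0.25) = 1.905, which the plan rounds to 1.9; difference 1 in absolute value; 75 evaluable per arm (280 × 0.8 / 3 = 74.7); two-sided alpha 0.025.

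**Validity of the current rule.** 0.025 + 0.025 = 0.05. With equal arms the two contrasts are orthogonal, so under the global null the family-wise error is about 1 − 0.975² = 0.0494. Control is sound.

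**The plan's own power figures.** Two-sided noncentral t with n1 + n2 − 2 degrees of freedom:

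- H2: noncentrality 1 / (1.9 × √(1/75 + 1/75)) = 3.22; power at 0.025 is 83.0%. The stated 83% reproduces.
- H1: noncentrality 1 / (1.9 × √(1/150 + 1/75)) = 3.72; power at 0.025 is 92.8% (92.6% with SD 1.905, 93.1% by normal approximation). The stated 90% does not reproduce. It would need an SD of about 2.0, which the plan does not use. A two-sided 0.0125 gives 88.5% for H1 but only 75.5% for H2, so it does not fit the pair.

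**Holm against Bonferroni.** Let a be power at 0.025 and b power at 0.05, with subscripts for H1 and H2. With orthogonal contrasts:

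- Holm power for H2 = a2 + a1(b2 − a2)
- Holm power for H1 = a1 + a2(b1 − a1)
- Both rejected: Bonferroni a1·a2; Holm a1·a2 plus the two gains above
- At least one rejected, either rule: 1 − (1 − a1)(1 − a2)

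Orthogonality is used only to compute power. Holm's error bound does not need it.

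*Single-visit inputs of 9.2, SD 1.9.* a1 = 0.9277, b1 = 0.9596, a2 = 0.8300, b2 = 0.8929. The gain for H2 is 0.9277 × (0.8929 − 0.8300) = 0.058, and for H1 0.8300 × (0.9596 − 0.9277) = 0.026. Both rejected: 0.770 + 0.058 + 0.026, or 0.855 before rounding.

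*Two-visit average.* The least-squares-means sentence in 9.4.2 points to an average over follow-up. The visit-to-visit correlation r is not in the documents; I assume 0.5 to 0.8, equal SDs at the two visits, baseline correlation 0.5 with each, and both visits observed. Given baseline, the correlation is (r − 0.25)/0.75 and the SD of the average is 1.905 × √((1 + that)/2). This gives 1.556 at r = 0.5 and 1.774 at r = 0.8.

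| Setting, difference −1 on both contrasts | H2 | H1 | Both | At least one |
|---|---|---|---|---|
| Single visit, SD 1.9 | 83.0% → 88.8% | 92.8% → 95.4% | 77.0% → 85.5% | 98.8%, unchanged |
| Two-visit, r = 0.8 | 88.1% → 92.7% | 95.8% → 97.5% | 84.4% → 90.8% | 99.5%, unchanged |
| Two-visit, r = 0.5 | 95.2% → 97.4% | 98.9% → 99.5% | 94.1% → 96.9% | 99.9%, unchanged |

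The first figure is Bonferroni, the second Holm. Simulation with a shared 222 degrees of freedom agrees within about 0.3 points.

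**What Holm costs.** With one null true and the other effect at −1, error on the true null is 0.025 × (1 + a of the other hypothesis), against 0.025 under Bonferroni:

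- H2 null: 4.8% (single visit), 4.9% (r = 0.8), 5.0% (r = 0.5)
- H1 null: 4.6%, 4.7%, 4.9%

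Under the global null both rules give 4.9%.

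The gains above are exactly the trials in which a hypothesis is rejected although its 97.5% interval includes zero: 8.5% (single visit), 6.4% (r = 0.8), 2.8% (r = 0.5).

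If H1 is null, the gain for H2 is 0.025 × (b2 − a2), between 0.06 and 0.16 percentage points.

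**The case against.** The strongest reply is that nothing is wrong. The level is pre-specified, its reason is stated, and design and analysis use the same 0.025. Bonferroni caps the error at 2.5% on each of two separate questions. Holm roughly doubles the chance of a false claim on one of them when the other effect is real; for example, a false claim that professional support adds benefit goes from 2.5% to 4.8% on the single-visit inputs. Bonferroni also has simple matching intervals. All of this stands, and it is why keeping the current rule for a stated reason is acceptable.

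The benefit is also conditional. It needs both effects to be real, and −1 on both contrasts means −1.5 with support and −0.5 without, each against duloxetine. Section 9.2 powers each aim separately and sets no joint target. On the two-visit average the gains are smaller and rest on an assumed correlation. These limits stand too, but they reduce the gain without removing it.

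Finally, the amendment history (Section 10.4) shows a trial under way by version 6 in July 2021, so relaxing a primary rule late may invite questions. That argues for making the change while blinded and recording the reason; it does not affect validity.

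**Conclusion.** The point holds as an inexpensive improvement. The current rule controls error correctly. At the same 5% bound, Holm would add 5.8 points of power for H2, 2.6 for H1 and 8.5 for establishing both on the inputs of Section 9.2. On the two-visit average the additions are 2.3 to 4.6, 0.6 to 1.8 and 2.8 to 6.4 points, for visit correlations from 0.5 to 0.8.

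These figures assume a true difference of −1 on both contrasts, 75 evaluable per arm, and one contrast per hypothesis on the average follow-up score. Separate tests at weeks 13 and 25 would enlarge the family.

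The Aim 1 power in Section 9.2 is understated by about 3 points. This is minor and conservative, has no effect on the sample size, and lends no weight to the case for Holm.

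**What to change.** Before unblinding, amend Section 9.4.2 so that H1 and H2 are tested by Holm's step-down procedure at a two-sided family-wise level of 0.05, in place of the fixed 0.025 for each. Report Holm-adjusted p-values with 97.5% intervals, and say in advance that a hypothesis rejected second, with p between 0.025 and 0.05, will have a 97.5% interval that includes zero. If the sponsor prefers Bonferroni for its matching intervals or its 2.5% limit on each hypothesis, keep it and state that reason. In Section 9.2, restate the Aim 1 power as about 93%, or as at least 90%.

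The change is to wording only: sample size, data collection and model stay as they are. It needs an amendment made while blinded, and it carries the two statistical costs quantified above.

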9.4.3 ANALYSIS OF THE SECONDARY ENDPOINT(S)

Secondary Outcomes

The secondary outcomes will include the two individual components of the BPI GPS: BPI pain severity and BPI pain interference. We will use similar LMMs described for the primary outcome analysis.

9.4.4 SAFETY ANALYSES

N/A

9.4.5 BASELINE DESCRIPTIVE STATISTICS

N/A

9.4.6 PLANNED INTERIM ANALYSES

N/A

9.4.7 SUB-GROUP ANALYSES

Subgroup Analyses

We will conduct subgroup analysis using LMMs to test the interactions between intervention arm (with and without health care professional support vs. monotherapy) and baseline characteristics. The subgroups include comorbid psychological distress, use of opioid, and number of painful body sites (dichotomized at the median value). The interaction will be tested at the 0.10 level of significance. A significant interaction is indicative of potential moderating effect of baseline characteristic such as psychological distress for predicting the mean BPI GPS score under combination therapy.

9.4.8 TABULATION OF INDIVIDUAL PARTICIPANT DATA

N/A

9.4.9 EXPLORATORY ANALYSES

Tertiary outcomes

We propose the following 4 tertiary outcomes to further assess the effect of the interventions on pain. We will use similar LMMs described for the primary outcome analysis.

1. *GRC*

GRC assesses overall clinical response. It is consistent with the IMMPACT recommendations for a 7-item patient global change scale⁵⁹. Modified to detect finer gradations of improvement, this scale is sensitive to treatment-related improvements

2. PROMIS pain intensity

3. PROMIS pain interference

PROMIS (<http://www.healthmeasures.net/explore-measurement-systems/promis/intro-to-promis>) Adult Self-Reported Measures on physical health (fatigue, pain intensity, pain interference, physical function, sleep disturbance, pain behavior and sleep-related impairment) and social health (ability to participate in social roles and activities). PROMIS measures were developed and validated with state of the science methods to be psychometrically sound (<http://www.healthmeasures.net/explore-measurement-systems/promis/measure-development-research>).

4. CPCI

Exploratory outcomes

1. *GAD-7*

GAD-7 is a validated screening and severity measure for the most common anxiety disorders in primary care (i.e., generalized anxiety, panic, social anxiety, and post-traumatic stress disorder)^{61,62}. Higher scores on *GAD-7* represent more severe anxiety symptoms. Clinical anxiety is defined as *GAD-7* score of ≥ 10 , a cut point validated in previous studies^{61,62}.

2. *PHQ-8*

PHQ-8 is a brief self-administered scale that assesses major depressive disorder core symptoms and allows a score (range: 0 to 24) based on the total number and severity of depressive symptoms noted over the previous two-week period. Its validity (including telephone mode of delivery), feasibility and capacity to detect changes of depressive symptoms over time are well established⁶³⁻⁶⁶. Clinical depression is defined as *PHQ-8* score of ≥ 10 , a cut point validated in prior studies

3. PCS

PCS is a 13-item scale that describes the catastrophic thoughts and feelings that people may have in response to pain. The psychometric properties of PCS are well established⁷⁰⁻⁷² including sensitivity to change^{73,74}. The total score ranges 0 (no catastrophizing) to 52 (severe catastrophizing).

4. **SF 36 physical function**

~~This 10-item scale inquires about the subject's perception of their limitations in the performance of various types of physical activities. Scale scores can range from 0 to 100, with higher scores indicating better functioning.~~

4. PROMIS Adult measures: The weight of evidence supports the appropriateness of using PROMIS measures across different medical conditions including various CMP conditions⁸⁵.

Physical function

Fatigue

Social health

Sleep disturbance

Pain behavior

5. **OME**

OME is a measure of daily dose of opioid use. We will use self-reported opioid type^{75,76}, medical record-based dosage and self-reported daily frequency to calculate the OME, reported in milligrams per day. The OME is calculated by multiplying dosage by daily frequency by a conversion factor for each opioid based on opioid strength⁷⁷.

6. **Health care service utilization**

We will extract data on use of different allied health care services from date of enrollment until the one-year anniversary utilizing EMR. The general approach will include models for count data. Length of follow-up will be used as an offset. Poisson models will be used to estimate the mean number of events for each intervention group. Alternatively, negative binomial (NB) models will be used if there is evidence of over-dispersion in model diagnostics. The specific health care utilization measures include the following.

7.1 Number of new referrals to other specialties or allied health services from enrollment date to the one-year anniversary

- a. Orthopedic surgery
- b. Spine center
- c. Neurosurgery
- d. Pain specialty
- e. Physical Medicine/Rehabilitation (PMR)
- f. Rheumatology
- g. Integrative Medicine
- h. Psychiatry
 - i. Medication
 - ii. Counseling
 - iii. Medication + counseling
- i. Quartet system for PCP – psychiatry/psychology referral (not currently linked with Wake One)
- j. Physical therapy
- k. Occupational therapy

7.2 Number of visits to each specialty or allied health services from enrollment date to the one-year anniversary

- l. Orthopedic surgery
- m. Spine center

- n. Neurosurgery
- o. Pain specialty
- p. Physical Medicine/Rehabilitation (PMR)
- q. Rheumatology
- r. Integrative Medicine
- s. Psychiatry
 - i. Medication
 - ii. Counseling
 - iii. Medication + counseling
- t. Quartet system for PCP – psychiatry/psychology referral (not currently link with Wake One)
- u. Physical therapy
- v. Occupational therapy

7.3 Number of orthopedic or musculoskeletal surgeries from enrollment date to the one-year anniversary. See attached relevant CPT codes.

8 *PHQ-ADS* is a composite of PHQ-8 and GAD-7 scores. PHQ-ADS is a single measure for assessing psychological distress in clinical practice and research ⁷⁸. This is especially salient given the frequent co-occurrence of depression and anxiety. PHQ-ADS cut points of 10, 20 and 30 were shown to represent mild, moderate, and severe levels of psychological distress, respectively. We are using cut point of ≥ 20 to represent moderate level of psychological distress.

9 *Frequency of Practicing Pain Coping Skills*. During the outcome data collection at weeks 13 and 25 we will ask participants how many days they practiced pain coping skills in the past 2 weeks (maximum of 14)³.

10 *Others*. The study will track medication use but will not control or restrict medication use as part of the study. To assess co-intervention effect, a treatment survey will inquire about specific treatments the patient has received (opiates and other analgesics, psychotropic medications and use of complementary and integrative health modalities such as acupuncture) for pain since the last follow-up ⁶⁹.

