1.3 SCHEDULE OF ACTIVITIES

Table 1. Study Measures and Time Points for Data Collection in PRECICE

Telephone Contacts/Visits ^a	Pre-Screening Visit	Week 0	Week 1	Week 2	Week 3	Week 4	Week 6	Week 10	Week 13	Week 14	Week 18	Week 22	Week 25	PRN
Type of Contact/Visit ^{b,c}	TC	IPV	IPV	TC	TC	TC	TC	TC	IPV	TC	TC	TC	IPV	PRN
Screening														
Phone Pre-Screening	✓													
Randomization			✓											
Physical Measures														
Blood Pressure	✓	✓							✓				✓	
Height	✓												✓	
Weight	✓												✓	
Urine Pregnancy Test	✓								✓					
Questionnaires														
3-item Pain Intensity Interview	✓								✓				✓	
Compiled Questionnaires		✓							✓				✓	
o Brief Pain Inventory														
o Generalized Anxiety Disorder (GAD-7)														
o Patient Health Questionnaire (PHQ8)														
o Global Rating of Change (GRoC)														
o Pain Catastrophizing Scale (PCS)														
o PROMIS Adult Self-Report														
o Chronic Pain Coping Inventory (CPCI)														
Demographics with Medical Diagnosis		✓												
Informed Consent		✓												
Missed Visit Form													✓	
Modified Pain Detect	✓													
Non-study Medication List	✓								✓				✓	
Nurse Counselling Tracking Form						✓		✓	✓		✓	✓	✓	
Opioid Risk Tool	✓													
Participant Status													✓	
Serious Adverse Event Report Form													✓	
Study Drug Accountability Log	✓ ^d	✓ ^e								✓			✓ ^f	
Study Medication Modification				✓						✓			✓ ^g	
Study Medication Symptom Monitoring Form		✓ ^h	✓ ⁱ			✓ ⁱ			✓ ⁱ		✓		✓ ^j	
TAPS – Tobacco, Alcohol, Prescription	✓												✓	
EMR Health Care Utilization ^h														

^a Weeks with participant contact are listed on this table.

^b IPV indicates in-person visit.

^c TC indicates telephone contact.

^d At study entry, all participants will receive duloxetine 30 mg once daily for one week.

^e At week 1, participants will receive duloxetine 60 mg once daily for 24 weeks.

^f At week 25, all participants will be provided duloxetine 30 mg once daily for 7 days and medication treatment will then stop (tapering regimen).

^g Phone administration on as needed basis only if participant calls the research office and complains of a potential side effect.

^h EMR Health Care Utilization will be collected at one year after randomization.

ⁱ Option of using text messaging as an adjunct to phone calls to assess duloxetine symptoms monitoring at weeks 2 and 4.

Revised 07/19/2021

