6.3 MEASURES TO MINIMIZE BIAS: RANDOMIZATION AND BLINDING

The PI and the analysis team at the clinical site will remain blinded to group assignment throughout the study. Randomization will be stratified by number of pain sites (≤ 2 vs. ≥ 3 sites) and opioid use. Number of pain sites is included as a stratification variable, since it has been associated with worse outcomes ⁸¹⁻⁸³.

The data team , who is blinded of treatment group assignment, has the primary responsibility of analyzing outcome data throughout the study.

Randomization will be accomplished through the REDCap Randomization Module. REDCap helps implement a defined randomization model within the study project, by allowing users to 1) Define all of the randomization parameters; 2) Create and upload a custom randomization table (i.e., allocation list). The table serves as a lookup table for deciding how to randomize subjects/records. The module also monitors the overall allocation progress and assignment of randomized subjects.

For more randomization details, see MOP chapter 07, Randomization.

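### The utilization count models name neither the randomization strata nor prior-year use; adjusted totals would be more precise, and rare service lines are better left descriptive

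*Combined protocol and SAP*

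**What the plan says.** Section 9.4.9 (Exploratory Analyses, Health care service utilization) sets out the model in a few sentences, and the objectives table in section 3 repeats them. Data are extracted "from date of enrollment until the one-year anniversary utilizing EMR". The model is Poisson: "Poisson models will be used to estimate the mean number of events for each intervention group". There is a fallback: "Alternatively, negative binomial (NB) models will be used if there is evidence of over-dispersion in model diagnostics". The only other model term is exposure: "Length of follow-up will be used as an offset".

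The measures follow under three items:

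- 7.1: "Number of new referrals to other specialties or allied health services from enrollment date to the one-year anniversary", with lettered lines a to k
- 7.2: "Number of visits to each specialty or allied health services from enrollment date to the one-year anniversary", with lettered lines l to v
- 7.3: a single count of orthopedic or musculoskeletal surgeries

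The section gives no covariates, expected rates or pooled visit total, and no rule for lines with few or no events.

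Section 6.3 states that "Randomization will be stratified by number of pain sites" (two or fewer versus three or more) and by opioid use. The primary model in section 9.4.2 includes the baseline BPI global score, opioid use and number of pain sites. The secondary and tertiary outcomes are to use similar mixed models. The count models carry no such cross-reference.

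**The concern.** Patients differ widely in how much care they use, and much of that difference usually persists from one year to the next. A count model with only arm and follow-up time leaves this variation in the error. The plan follows a different principle for its primary outcome, where section 9.4.2 justifies baseline adjustment by efficiency, precision and power. Leaving out the stratification factors also departs from the design and from the primary model.

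The second issue is sparsity. Some of the listed services may be used by very few trial patients within a year. If one arm has no events on a line, the log-link rate ratio against that arm is infinite. The negative binomial fallback deals with over-dispersion. It neither recovers lost precision nor helps an empty arm.

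At stake are wider intervals than necessary for utilization, and unplanned decisions after the data are seen about which lines to model and how to handle failed fits.

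**Working it through.** The plan states no rate, power or precision for utilization, so it has no figure to reproduce. Event rates, over-dispersion and correlations below are assumptions.

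**Inputs from the documents.** Section 9.2 gives 280 participants in three arms, so 280/3 ≈ 93 per arm. With 20% loss this becomes 280 × 0.8/3 = 74.7, about 75. The lettered measures number 11 + 11 + 1 = 23.

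**Why adjustment helps only common outcomes.** For mean count μ per year and over-dispersion k, the variance of a log rate ratio between two arms is approximately (1/μ + k)(1/n₁ + 1/n₂). Covariates can reduce only k. Take k = 2, 93 per arm, and covariates that explain a quarter of k:

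- μ = 1: (1 + 2)(2/93) = 0.0645 falls to (1 + 1.5)(2/93) = 0.0538, a cut of 16.7%.
- μ = 0.05: (20 + 2)(2/93) = 0.473 falls to (20 + 1.5)(2/93) = 0.462, a cut of 2.3%.

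**Simulated cut in variance, mean 1 to 3 events per year, 93 per arm.** Simulation A used log-normal frailty, a rate ratio of 0.7 and a negative binomial model with robust standard errors, with 500 trials per setting. It added the log prior-year count, log(1 + count). Simulation B used k = 2, a stratum rate ratio of 1.5 and a Poisson model. It added both strata and the log prior-year count.

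| Year-to-year correlation | A | B |
|---|---|---|
| 0.3 | 2–9% | 1–3% |
| 0.5 | 11–22% | 6–10% |
| 0.7 | 16–45% | not run |
| 0.8 | not run | 24–40% |

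In simulation B at mean 3, the standard deviation of the estimate fell from 0.212 to 0.202 at correlation 0.5, and from 0.234 to 0.182 at 0.8. Strata alone cut the variance by about 0–2%. At means of 0.05 to 0.2, full adjustment changed the variance by between −0.5% and +1.6%, which is effectively nothing.

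**Empty arms.** Under Poisson with 93 per arm, the chance that a given arm has no events is e^(−93μ). The chance that at least one of three arms has none is 1 − (1 − e^(−93μ))³.

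| μ per year | Given arm | Any of three arms |
|---|---|---|
| 0.01 | 39% | 78% |
| 0.02 | 16% | 40% |
| 0.05 | 1% | 3% |
| 0.10 | under 0.1% | under 0.1% |

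With 75 per arm, the any-arm risk is 85% at 0.01 and 53% at 0.02. Negative binomial counts with k up to 10 raise the 93-per-arm figures only modestly (40% becomes 46% at 0.02).

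**Pooling.** Eleven lines at 0.02 each sum to 0.22 events per patient. The chance that a given arm is empty is then e^(−93 × 0.22) ≈ 1e-9 under Poisson. For a negative binomial with k = 5 it is (1 + 5 × 0.22)^(−93/5) ≈ 1e-6. Adjustment therefore improves the totals, and pooling resolves sparsity.

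**The case against.** The strongest reply is that section 9.4.9 describes a general approach and is silent on covariates, which does not exclude them. Randomization protects the unadjusted rate ratio from confounding, so only precision is lost. The outcome is exploratory. Every magnitude above rests on rates absent from the documents, and one of the two proposed covariate sets, the strata, gains almost nothing. All of this stands and limits the weight of the point.

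Prior-year records may also be incomplete. Sections 1.1 and 5.5 allow recruitment through providers outside the health system, and the Quartet referral line is described as not linked to the record system. A prior-year zero may then mean not recorded, which would weaken the covariate. This stands too, although the same gap affects the planned outcome.

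A reader might infer four stronger criticisms that the documents do not support:

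- **46 tests.** Multiplying 23 measures by two contrasts gives 46 tests and 46 × 0.05 = 2.3 expected false positives. The plan sets no contrast, hypothesis or alpha for utilization. H1 and H2 concern BPI GPS.
- **23 separate models.** Only item 7.2 refers to each specialty. Item 7.1 can be read as one total, with the letters listing what qualifies.
- **An undefined new referral.** Counted from enrollment, a new referral plainly means one made after enrollment. A look-back would define a different outcome.
- **A contradictory window.** Footnote h of Table 1 says "EMR Health Care Utilization will be collected at one year after randomization", which may only date the extraction. If one pre-randomization week is counted in all arms, a rate ratio of 0.70 becomes (0.7 × 51 + 1)/52 ≈ 0.706. This is at most a wording point.

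**Conclusion.** The point holds as a minor improvement in precision and prespecification. As written, the count models name only arm and follow-up time, while the plan's primary model adjusts for baseline and both strata. With a log link, and absent interaction, adjustment does not change what the rate ratio means, so the proposed covariates bring precision without changing the question.

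For totals averaging 1 to 3 events per year, the expected variance reduction is about 1–9% at a year-to-year correlation of 0.3, 6–22% at 0.5 and 16–45% at 0.7–0.8. Nearly all of it comes from prior-year use. The case for the strata is consistency with the design. Single lines averaging about 0.02 events per year or fewer carry a 40% or higher chance of an empty arm, and covariates do not help them. Whether any line is that rare cannot be told from the documents; the unlinked Quartet line is the only documented reason to expect missing or zero counts. No primary or secondary conclusion is affected.

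**What to change.** In section 9.4.9:

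1. Prespecify three modelled outcomes: total referrals, total visits, and surgeries.
2. In each model include arm, opioid use, the pain-site stratum, log(1 + the matching count in the 12 months before enrollment) from the same EMR extraction, and the follow-up offset. Keep the negative binomial fallback.
3. Report individual service lines as counts and means by arm, without models.
4. State a minimum event count for fitting a model. Surgery is a single line and may itself be rare; if an arm has no events, report counts only.
5. State how patients without a usable prior-year record are handled, and whether the Quartet line enters the totals.
6. As minor wording, say whether the counting window starts at enrollment or at randomization.

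The cost is a few sentences of SAP text and one more year in an extraction already planned. The downsides are possibly incomplete prior-year data for patients of outside providers and no formal test per service line.
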